6.1. Adverse Events

The verbatim terms used in the CRF by investigators to identify adverse events will be coded using the Medical Dictionary for Regulatory Activities (MedDRA). Any AE starting at or after the initial administration of study agent through the end of the trial is considered to be treatment emergent. If the event occurs on the day of the initial administration of study agent, and either event time or time of administration are missing, then the event will be assumed to be treatment emergent. If the event date is recorded as partial or completely missing, then the event will be considered to be treatment emergent unless it is known to be prior to the first administration of study agent based on partial onset date or resolution date. All reported treatment-emergent adverse events will be included in the analysis.

Infusion Reactions

A comprehensive clinical review of all AEs that occurred on the same day of infusion, with a start time during infusion or ≤ 60 minutes after the end of IV infusion of study agent (AEs temporally related to infusion), with the exception of laboratory abnormalities, will be performed to identify the occurrence of potential infusion reactions. Specifically, the reported AEs temporally related to infusion will be reviewed to identify participants with a contemporaneous constellation of AE terms that are consistent with the signs or symptoms that typically occur during hypersensitivity reactions or cytokine release syndromes (eg, anaphylaxis, fever, chills, rigors, hypotension,

hypertension, bronchospasm, laryngospasm, wheezing, dyspnea, syncope, pre-syncope, urticaria, angioedema, generalized pruritus, flushing, rash, and nausea), to identify all participants with potential infusion reactions.

Injection-site Reactions

A study intervention injection-site reaction is any adverse reaction at an SC study intervention injection-site. The injection sites will be evaluated for reactions and any injection-site reactions will be recorded as an AE.

Any unfavorable or unintended sign that occurs at the injection (infusion) site is an injection site reaction and will be recorded as an injection site reaction by the investigator on the eCRF

Infection

An infection is defined as any AE that was recorded as an infection by the investigator on the eCRF.

The following analyses will also be used to assess the safety of participants in the study:

- The incidence and type of AEs.
- The incidence and type of SAEs.
- The incidence and type of infections.
- The incidence and type of reasonably related AEs.
- The incidence and type of AEs temporally associated with infusion (defined as an AE that occurred on the same day of infusion, with a start time during infusion or ≤ 60 minutes after the end of infusion).
- The incidence and type of injection-site reactions.

These summary tables will provide the count and percentage of participants with 1 or more of the specified AEs by treatment group. In addition to the summary tables, listings will be provided for participants who:

- Had SAEs.
- Had AEs leading to discontinuation of study agent administration.
- Had AEs of severe intensity.
- Had treatment-emergent adverse events temporally associated with infusion.
- Had anaphylactic or serum sickness-like reactions.

Since safety should be assessed relative to exposure and follow-up, most AE summary tables will include average weeks of follow-up and average number of study agent administrations, infusions and injections for each treatment group. A listing of participants who died will be provided.

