6. STUDY INTERVENTION

6.1. Study Interventions Administered

All participants will receive 1 IV infusion at Weeks 0, 4, and 8 (either active or placebo).

All participants will receive 2 SC injections at each visit (either active, active and placebo, or placebo) every 4 weeks from Weeks 0 to 36.

Intravenous study intervention should be administered over a period of not less than 1 hour, and not more than 2 hours. The infusion should be completed within 6 hours of preparation.

Since 2 SC injections will be administered at each administration visit, each SC injection should be given at a different location of the body.

Detailed instructions on the administration of IV and SC study intervention will be provided in the Site Investigational Product (IP) Binder.

Study intervention administration must be captured in the source documents and the electronic case report form (eCRF).

Guselkumab and placebo will be manufactured and provided under the responsibility of the sponsor. Refer to the IB for a list of excipients.

For details on rescue medications, refer to Section 6.5.1. For a definition of study intervention overdose, refer to Section 8.4, Treatment of Overdose.

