1.2. Trial Design

This is a Phase 2, multicenter, randomized, placebo-controlled, double-blind, proof-of-concept (POC) study evaluating the efficacy, safety, PK, and immunogenicity of SC and IV administered guselkumab for the treatment of moderate to severe HS in adult participants. The participant population will comprise men and women who have had moderate to severe HS for at least 1 year.

A diagram of the study design ([Figure 1](#)) is provided below and as depicted in [Figure 1](#), approximately 180 participants who satisfy all inclusion and exclusion criteria will be randomized in a 1:1:1 ratio to 1 of 3 groups:

Group 1: Guselkumab Regimen 1 (1200 mg IV q4w x 3 → 200 mg SC q4w)

Participants will receive guselkumab 1200 mg IV at Week 0, Week 4, and Week 8 (ie, a total of 3 IV guselkumab doses and 3 SC placebo doses). At Week 12, participants will continue treatment with guselkumab 200 mg SC q4w through Week 36.

Group 2: Guselkumab Regimen 2 (200 mg SC q4w x 3 → 200 mg SC q4w)

Participants will receive guselkumab 200 mg SC at Week 0, Week 4, and Week 8 (ie, a total of 3 SC guselkumab doses and 3 IV placebo doses). At Week 12, participants will switch treatment to guselkumab 200 mg SC q4w through Week 36.

Group 3: Placebo

[figure not shown]
Participants will receive placebo IV and SC at Week 0, Week 4, and Week 8 (ie, a total of 3 IV and 3 SC placebo doses) and an additional SC placebo dose at Week 12. At Week 16, participants will be rerandomized in a 1:1 ratio to either guselkumab 200 mg SC q4w through Week 36 or guselkumab 100 mg SC at Weeks 16, 20, 28, and 36, and placebo at Weeks 24 and 32.

A screening period will take approximately 4 weeks. All participants will enter safety follow-up after Week 36 through Week 48. Two planned database locks (DBLs) will occur, at Week 16 and at Week 48.

Efficacy assessments (HS-IGA, lesion counts, Hurley staging, Hidradenitis Suppurativa Symptom Diary [HSSD], Dermatology Life Quality Index [DLQI], Hospital Anxiety and Depression Scale [HADS], and Patient's Global Impression of Change [PGIC]) will be performed according to the Schedules of Activities. Serum samples for PK, immunogenicity, and biomarker analyses will be collected at the timepoints shown in the Schedules of Activities (Section 1.3 of the protocol).

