6. SAFETY

Safety will be assessed by summarizing the incidence and type of AEs and examining changes in laboratory parameters (hematology and chemistry), vital signs, and suicidal ideation and behavior as measured by the C-SSRS (Columbia-Suicide Severity Rating Scale).

In all the safety analysis, randomized participants who received at least 1 (partial or complete) dose of study agent administration will be included and analyzed according to the treatment they actually received, regardless of the treatments they are randomized to. No formal statistical comparison is planned.

Depending on the safety data categories, the cumulative safety data will be analyzed through different study periods through Week 16 and Week 48. Unless otherwise specified, tabular summaries of safety events for key study periods are in general presented as following:

Summaries through Week 16 (placebo controlled):

Safety data through Week 16 will be summarized by treatment groups

1. Placebo
2. Guselkumab 200 mg SC
3. Guselkumab 1200 mg IV
4. Combined Guselkumab

This allows between-group comparisons of safety between the guselkumab regimens and the placebo group based on similar follow-up period in each group.

Summaries through Week 48

Safety data through Week 48 will be summarized by treatment groups including

1. Placebo → guselkumab 100 mg SC
2. Placebo → guselkumab 200 mg SC
3. Guselkumab 200 mg SC
4. Guselkumab 1200 mg IV
5. Combined Guselkumab

This allows safety comparisons between each guselkumab regimen through Week 48 based on the similar follow-up time in each group.

The list of actual treatment groups for safety analyses and inclusions of participants and safety events/measurements in each group are defined as follows:

1. **Placebo:** all participants who were randomized to placebo at Week 0 and received treatment with placebo only or received treatment with placebo prior to receiving treatment with guselkumab. For participants who started treatment with placebo but later received

guselkumab, the safety events/measurements on and after the first dose of guselkumab will be excluded from this group. Only the safety events/measurements that occurred while the participants had been receiving placebo only will be included in this group.

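### The Combined Guselkumab column mixes active and placebo administrations in the infusion and injection-site tables, and two regimen columns count reactions to placebo injections

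*SAP*

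**What the plan says.** SAP 6.1 lists, among its safety analyses, adverse events temporally associated with infusion (defined by timing alone, up to 60 minutes after the infusion ends) and injection-site reactions. Of the tables it says: "These summary tables will provide the count and percentage of participants with 1 or more of the specified AEs by treatment group". SAP 6 sets the default columns, and both the Week 16 and the Week 48 layouts end with "Combined Guselkumab". The list of group definitions in SAP 6 takes all events from Week 0 into the two guselkumab arms, whatever product preceded them. It does not define the Combined group.

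The design is double-dummy. Protocol 6.1 states "All participants will receive 1 IV infusion at Weeks 0, 4, and 8 (either active or placebo" and "All participants will receive 2 SC injections at each visit (either active, active and placebo, or placebo". Per SAP 1.2, over Weeks 0, 4 and 8 the 1200 mg IV group receives "a total of 3 IV guselkumab doses and 3 SC placebo doses" and the 200 mg SC group "a total of 3 SC guselkumab doses and 3 IV placebo doses". One crossover group receives "guselkumab 100 mg SC at Weeks 16, 20, 28, and 36, and placebo at Weeks 24 and 32".

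On definitions, SAP 6.1 first confines an injection-site reaction to a subcutaneous injection site, as Protocol 8.2.10 does. Its next paragraph then says: "Any unfavorable or unintended sign that occurs at the injection (infusion) site is an injection site reaction".

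**The concern.** Infusion-associated events and injection-site reactions are tied to a route. In a double-dummy trial a participant in a guselkumab column may have received only placebo by the route in question. A pooled guselkumab percentage for infusion events then averages active and placebo infusions, and a regimen's injection-site percentage can include reactions to placebo syringes.

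Safety and tolerability are part of the primary objective (SAP 1.1). The trial gives 1200 mg IV three times, while the highest single IV dose the protocol reports as already studied is 987 mg (Protocol 2.2 and 4.3). A pooled infusion figure is the kind of number that gets carried into a summary without its footnotes.

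**Working it through.** **Inputs.** 60 participants per arm (SAP 1.4). Infusions at Weeks 0, 4 and 8 in every arm, and 2 SC injections per visit every 4 weeks from Week 0 to Week 36 (Protocol 6.1). Content by arm as in SAP 1.2. The documents give no reaction rates, so all rates below are assumptions shown over a range.

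**1. The plan's own counts.** Three visits (Weeks 0, 4, 8) with one infusion each give 3 active infusions and 3 placebo SC doses in the 1200 mg IV arm, and the reverse in the 200 mg SC arm. This reproduces SAP 1.2.

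**2. Infusions in the Combined column through Week 16.** Active: 60 × 3 = 180. Placebo: 60 × 3 = 180. Placebo share: 180/360 = 50%. The 1200 mg IV column alone is 180 of 180 active.

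**3. Effect on the infusion-event percentage.** With participant-level rates *a* (active) and *p* (placebo), Combined = (60*a* + 60*p*)/120:

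| *a* | *p* | 1200 mg IV column | Combined, Week 16 |
|---|---|---|---|
| 5% | 2% | 5% | 3.5% |
| 10% | 3% | 10% | 6.5% |
| 15% | 5% | 15% | 10% |
| 10% | 10% | 10% | 10% |

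The pull is toward placebo whenever *a* > *p*, and vanishes when they are equal.

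**4. Injections per participant.** Assuming 100 mg per syringe, which fits the three content options in Protocol 6.1:

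| Column | Weeks | Active | Placebo |
|---|---|---|---|
| 1200 mg IV | 0–12 | 2 | 6 |
| 200 mg SC | 0–12 | 8 | 0 |
| Placebo to 100 mg | 16–36 | 4 | 8 |
| Placebo to 200 mg | 16–36 | 12 | 0 |

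Without that assumption, 3 × 2 = 6 of 8 (Weeks 0, 4, 8) in the 1200 mg IV arm and 2 × 2 = 4 of 12 (Weeks 24, 32) in Placebo to 100 mg are still placebo for certain. Combined over Weeks 0–12 holds 60 × (2 + 8) = 600 active and 60 × 6 = 360 placebo injections, so 360/960 = 37.5% placebo.

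**5. Direction of the injection-site effect.** With independent per-injection rates *qa* (active) and *qp* (placebo), the chance of at least one reaction in the 1200 mg IV arm over Weeks 0–12 is 1 − (1 − *qa*)² (1 − *qp*)⁶. From its two active injections alone it is 1 − (1 − *qa*)².

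| *qa* | *qp* | All 8 injections | 2 active only |
|---|---|---|---|
| 2% | 0.5% | 6.8% | 4.0% |
| 2% | 1% | 9.6% | 4.0% |
| 3% | 1% | 11.4% | 5.9% |

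Placebo injections raise the planned statistic. They would lower only a per-injection rate, for example (2 × 2% + 6 × 1%)/8 = 1.25% against 2%, which the SAP does not plan to report.

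**6. Week 48, conditional.** Crossover groups count events only from their first guselkumab dose, and infusions end at Week 8, so their infusion-event count is zero by construction. If an infusion table is produced through Week 48, and Combined takes in all crossovers (about 180 in total), the 10%/3% case reads (6 + 1.8)/180 = 4.3%.

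**The case against.** The regimen columns are legitimate. Through Week 12 every arm has 3 infusions and 8 injections, so each guselkumab-versus-placebo contrast is balanced. The 1200 mg IV infusion column is entirely active and sits beside two columns whose infusions are all placebo, so the rate of most interest can be read directly. Infusion-associated events are also listed by participant, potential infusion reactions get a clinical review, and most adverse event tables show average infusions and injections. No formal safety comparison is planned.

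All of that stands, and it rules out a reading that a reader might infer: that the by-regimen layout dilutes guselkumab's own reaction rates. For infusions, dilution occurs only in the Combined column. For injections within a single column, placebo syringes push the reported percentage up.

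Nor can every infusion-timed event in the 200 mg SC arm be blamed on the placebo infusion. Those participants receive SC guselkumab at the same visits, and the definition rests on timing alone. That arm should therefore not be pooled with placebo.

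The mitigations do not reach the residue. The exposure lines are not split into active and placebo. SAP 6.1 plans no listing of injection-site reactions, and the SAP 7.2.1 listing that shows them covers antibody-positive participants only.

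**Conclusion.** The point holds for three items.

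- **Combined column, infusion events.** Half of its infusions through Week 16 are placebo by design, so the percentage lies midway between the two arms' rates.
- **Injection-site reactions.** The 1200 mg IV column (6 of 8 placebo through Week 12) and the Placebo to 100 mg column (4 of 12 for certain, 8 of 12 if each active syringe is 100 mg) include reactions to placebo injections.
- **Definition.** The infusion wording in SAP 6.1 contradicts the sentence before it and Protocol 8.2.10. It would, for example, let a placebo infusion-site sign count in the 200 mg SC column, where every SC injection is active.

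The counts follow from the schedule. The percentages rest on assumed rates and, for injections, on independence and 100 mg per syringe. A reader might also infer a specific Week 48 dilution, but the SAP neither defines Combined nor commits to an infusion table through that week, so that figure is only conditional. These are reporting matters; power, alpha and the efficacy analyses are unaffected.

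**What to change.** In SAP 6 and 6.1:

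- **Infusion-associated events:** drop Combined Guselkumab, or restrict it to participants who received guselkumab IV. As planned, the restricted column would repeat the 1200 mg IV column, so dropping is simpler. Keep the three arms separate and label each with the content infused, noting that the 200 mg SC arm has SC guselkumab at the same visits.
- **Injection-site reactions:** add a breakdown by whether that visit's injections contained any guselkumab or placebo only, with matching denominators. Describe it as content given, not cause.
- **Definition:** delete the parenthetical reference to infusion from the injection-site reaction definition.
- **Combined Guselkumab:** state its membership wherever it is kept.

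The cost is SAP wording and two re-specified tables. Infusion times, injection dates and locations, and the intervention number are already recorded (Protocol 6.3 and 6.4). One limitation should be footnoted: in the 1200 mg IV arm, content is partly confounded with visit, because Weeks 0–8 are placebo only and guselkumab injections start at Week 12.

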6.2. Clinical Laboratory Tests

All clinical laboratory reports will be displayed for the participants included in the safety analysis set. The clinical laboratory parameters to be evaluated by the central laboratory include but are not limited to:

- **Hematology:** hemoglobin, hematocrit, lymphocytes, neutrophils, platelets, red blood cell (RBC) count and white blood cell (WBC) count.
- **Chemistry:** albumin, alkaline phosphatase, alanine aminotransferase, aspartate aminotransferase, total bilirubin, blood urea nitrogen/urea, calcium, chloride, creatinine, glucose, potassium, total protein, sodium.

Box plots of laboratory measurements and change from baseline will be provided for the selected laboratory measurement.

Applicable laboratory results will be graded according to National Cancer Institute's Common Terminology Criteria for Adverse Events (NCI-CTCAE version 5.0). The worst NCI-CTCAE will be summarized by treatment group.

For non-fasting glucose, the screening measurement will be used as the baseline measurement. A listing of participants with 1 or more NCI-CTCAE toxicity grade ≥ 2 in hematology and clinical chemistry laboratory measurements will be provided

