Pharmacokinetics a	nd Immunoge	nicity ^{k,l}													
Serum guselkumab concentration		X	X	X	X	X	X	X		X			X		X
Antibodies to guselkumab		X	X	X	X		X			X			X		X
Biomarkers															
Serum biomarkers ^c		X		X			X						X		X

Footnotes:

- a. The screening visit should occur no more than 4 weeks before the Week 0 visit.
- b. The Early Termination Visit should occur approximately 12 weeks after the last administration of study intervention (unless consent is withdrawn).
- c. All study procedures and evaluations are to be completed before study intervention is administered except where otherwise indicated.
- d. Randomization at Week 16 is for placebo group only and will not affect blinding.
- e. IV infusions and SC injections for Weeks 0, 4, 8 and SC injections for Weeks 12 through 36.
- f. The C-SSRS should be completed as the first assessment at screening after signing informed consent and before any tests, procedures, or other consultations, with the exception of the urine pregnancy test, and as the first assessment for baseline and all post-baseline visits, before any tests, procedures, or other consultations, with the exception of the urine pregnancy test, to prevent influencing participant perceptions. DLQI, HADS, HSSD, and PGIC should be performed before any tests, procedures, or other evaluations (Hurley stage, HS-IGA, Lesion counts), with the exception of the urine pregnancy test, for that visit.
- g. Women of childbearing potential must have a negative urine pregnancy test result before randomization and before receiving study intervention at all study intervention administration visits, and at Week 48 or early termination visit.
- h. Photographs to be taken at selected sites for participants who provide an additional consent; if such participants discontinue administration of study intervention early, however, photographs are not required at the final study visit.
- i. A tuberculin skin test is additionally required if the QuantiFERON®-TB test is not approved/registered in the country in which this study is being conducted.
- j. Participants must fast (ie, no food or beverages [except water]) for at least 8 hours before blood is drawn for lipid panel.

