- e. Have a chest radiograph (both posterior-anterior and lateral views, or per country regulations where applicable), taken within 3 months before the first administration of study intervention and read by a qualified radiologist, with no evidence of current, active TB or old, inactive TB.
- 14. Agree not to receive a live virus or live bacterial vaccination during the study, or within 12 weeks after the last administration of study intervention. For information on Bacille Calmette-Guérin (BCG) vaccination, see Inclusion Criterion 15.

- 15. Agree not to receive a BCG vaccination during the study, or within 12 months after the last administration of study intervention.
- 16. Have screening laboratory test results within the following parameters, if one or more of the laboratory parameters is out of range, a single retest of laboratory values is permitted:

a.	Hemoglobin	≥10 g/dL	(SI: \geq 100 mmol/L)
b.	White blood cells	$\geq 3.5 \times 10^{3}/\mu L$	(SI: ≥3.5 GI/L)
c.	Neutrophils	$\geq 1.5 \times 10^{3}/\mu L$	(SI: ≥1.5 GI/L)
d.	Platelets	$\geq 100 \text{ x } 10^3 / \mu L$	(SI: ≥ 100 GI/L)
e.	Serum creatinine	\leq 1.5 mg/dL	(SI: $\leq 137 \mu \text{mol/L}$)

- f. Aspartate aminotransferase $\leq 2 \times \text{upper limit of normal (ULN)}$
- g. Alanine aminotransferase $\leq 2 \times ULN$
- h. Alkaline phosphatase $\leq 2 \times ULN$
- 17. Be willing and able to adhere to the prohibitions and restrictions specified in this protocol.
- 18. Must sign an informed consent form (ICF) indicating that he or she understands the purpose of and procedures required for the study and is willing to participate in the study.

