2. **Placebo → guselkumab 100 mg SC:** all participants who were randomized to placebo at Week 0 started treatment with placebo only and later randomized to treatment with guselkumab 100 mg SC q8w. Only the safety events/measurements from these participants that occurred on and after their first administration of guselkumab will be included in this group.
3. **Placebo → guselkumab 200 mg SC:** all participants who were randomized to placebo at Week 0 started treatment with placebo only and later randomized to treatment with guselkumab 200 mg SC q4w. Only the safety events/measurements from these participants that occurred on and after their first administration of guselkumab will be included in this group.
4. **Guselkumab 200 mg SC:** all participants who were randomized to guselkumab 200 mg SC q4w at Week 0 and received guselkumab. All the safety events/measurements from these participants that occurred from Week 0 will be included in this group.
5. **Guselkumab 1200 mg IV:** all participants who were randomized to guselkumab 1200 mg IV q4w at Week 0 and received guselkumab. All the safety events/measurements from these participants that occurred from Week 0 will be included in this group.

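### SAP 6.2 tabulates the worst laboratory toxicity grade with no post-dose or worsening-from-baseline condition, so stable abnormalities present at entry are counted in every column

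*SAP*

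**What the plan says.** SAP 6.2 grades applicable results by NCI-CTCAE version 5.0 and then states: "The worst NCI-CTCAE will be summarized by treatment group". The accompanying listing of grade 2 or higher results carries no baseline condition either. The baseline-related output in that section is box plots of change from baseline for selected measurements. Protocol 9.4.3 plans the incidence and severity of abnormal laboratory parameters by group and adds no comparison with the baseline grade.

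SAP 6 decides which measurements enter which column:

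- Guselkumab 200 mg SC and 1200 mg IV: "All the safety events/measurements from these participants that occurred from Week 0 will be included in this group".
- Placebo: "Only the safety events/measurements that occurred while the participants had been receiving placebo only will be included in this group". For participants who later cross over, "the safety events/measurements on and after the first dose of guselkumab will be excluded from this group".
- The two crossover columns: "Only the safety events/measurements from these participants that occurred on and after their first administration of guselkumab will be included in this group".

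The Schedule of Activities (Protocol 1.3) places hematology and chemistry at screening and Weeks 0, 16, 40 and 48 (or early termination). Its footnote c says: "All study procedures and evaluations are to be completed before study intervention is administered except where otherwise indicated". The Week 0 draw is therefore pre-dose, and under SAP 2.7 it is normally the baseline value itself.

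Other safety data are handled differently. SAP 6.1 has a treatment-emergent rule for adverse events. SAP 6.5 uses the maximum post-baseline C-SSRS outcome and adds a shift table.

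**The concern.** A table of worst grade by arm will be read as describing what happened on treatment. Without a post-dose limit or a comparison with the baseline grade, it mixes new toxicity with abnormalities that predate dosing.

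Such abnormalities can be present. Inclusion Criterion 16 opens with "Have screening laboratory test results within the following parameters" and then limits 8 analytes: hemoglobin, white cells, neutrophils, platelets, creatinine, AST, ALT and alkaline phosphatase, the last three only to twice the upper limit of normal. SAP 6.2 names 20 parameters (7 hematology, 13 chemistry), so 12 have no entry limit.

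Safety is part of the primary objective. The 1200 mg IV dose exceeds the highest single IV dose that Protocol 4.3 reports as previously tested (987 mg), although Protocol 2.3 notes that the same regimen is in use in a Crohn's disease program. With about 60 participants per arm, a modest laboratory signal is easily lost among entry abnormalities.

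**Working it through.** The plan gives no figure to reproduce. The check sets the windows against the draw schedule and then sizes the effect under assumed rates.

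**1. Scheduled draws per column, read literally.** The randomized guselkumab columns hold Weeks 0 and 16 in the placebo-controlled period (the pre-dose draw is 1 of 2 values) and Weeks 0, 16, 40 and 48 overall (1 of 4). The placebo column certainly holds Week 16; whether it also holds Week 0 is not stated. The crossover columns hold Weeks 40 and 48.

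**2. Stable abnormalities, matched windows.** Let b be the share abnormal at entry who neither resolve nor worsen, and r the rate of new abnormality among the rest. Assume r = 5% on placebo and 15% on guselkumab, with n = 60 per arm. Stable cases are seen again at Week 16, so they count whether or not Week 0 is in the window.

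- As planned: p = b + (1 − b)r. Worsening only, over all 60: p = (1 − b)r.
- SE = √[p₁(1 − p₁)/60 + p₂(1 − p₂)/60].

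For b = 20% as planned: 0.20 + 0.80 × 0.05 = 24% and 0.20 + 0.80 × 0.15 = 32%. Worsening only: 0.80 × 0.05 = 4% and 0.80 × 0.15 = 12%.

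| b | Rule | Placebo | Guselkumab | Difference (points) | SE (points) | Difference/SE | Ratio |
|---|---|---|---|---|---|---|---|
| 10% | planned | 14.5% | 23.5% | 9.0 | 7.12 | 1.26 | 1.62 |
| 10% | worsening | 4.5% | 13.5% | 9.0 | 5.16 | 1.74 | 3.0 |
| 20% | planned | 24.0% | 32.0% | 8.0 | 8.16 | 0.98 | 1.33 |
| 20% | worsening | 4.0% | 12.0% | 8.0 | 4.90 | 1.63 | 3.0 |
| 30% | planned | 33.5% | 40.5% | 7.0 | 8.79 | 0.80 | 1.21 |
| 30% | worsening | 3.5% | 10.5% | 7.0 | 4.61 | 1.52 | 3.0 |

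Within each b the difference is identical under both rules. Only the ratio and the noise change.

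**3. Abnormalities that resolve, conditional on unequal windows.** Suppose Week 0 counts for guselkumab but not for placebo, and there is no drug effect (r = 5% in both arms). Now let b be everyone abnormal at Week 0, and f the share of them normal by Week 16. Placebo = b(1 − f) + (1 − b)r; guselkumab = b + (1 − b)r; false excess = b × f. With b = 20%, guselkumab shows 24%. Placebo shows 19%, 14% or 9% for f = 25%, 50% or 75%, a false excess of 5, 10 or 15 points. If both columns use the same window, this excess is zero.

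**The case against.** The table is descriptive: SAP 6 says "No formal statistical comparison is planned", and neither a rate ratio nor a standardized difference is specified. Even under a worsening rule the illustrated difference/SE stays between 1.52 and 1.74, so no test conclusion would change. Clinically relevant laboratory changes are recorded as adverse events (Protocol 8.2.4) and fall under the treatment-emergent rule. Change-from-baseline displays are planned, and an independent committee reviews unblinded safety data. Only applicable results are graded and NCI-CTCAE is not supplied, so the number of unrestricted parameters that reach the table is unknown. The rule may also sit in data presentation specifications, which appear in the SAP's abbreviation list but are not available. All of this stands and limits the weight of the point. None of it corrects the graded counts.

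Three stronger readings are tempting, and the documents do not support them:

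- **Including Week 0 causes stable abnormalities to be counted.** It does not. They recur at Week 16 and are counted in every column regardless. Including Week 0 adds only abnormalities that later resolve.
- **The guselkumab columns are inflated relative to placebo.** This needs the placebo wording to exclude the pre-dose draw, which the plan does not settle. SAP 6 describes the Week 16 comparison as resting on similar follow-up in each group, which points to matched windows.
- **The Week 16 draw drops out of the placebo column at crossover.** This needs a cut by calendar date. The cut-off is the first guselkumab dose, the draw precedes dosing, and Protocol 6.4 and 8 have the times of injections and blood collections recorded. The draw belongs to placebo.

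**Conclusion.** The concern holds as a minor point. Following SAP 6.2 as written, stable laboratory abnormalities that predate dosing enter the worst-grade summary in every column. With matched windows the risk difference is unchanged; for 10% to 30% abnormal at entry, an underlying ratio of 3.0 appears as 1.62 to 1.21, and difference/SE falls from 1.74–1.52 to 1.26–0.80. These figures rest on assumed rates and on collapsing the grades to any abnormality.

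Separately, the Week 0 wording for the randomized guselkumab columns brings in pre-dose abnormalities that resolve. The 5 to 15 point excess is conditional on one unsettled reading of the placebo column as well as on assumed rates, and should not be quoted as a property of the plan.

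**What to change.** In SAP 6.2:

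- Summarize the worst grade after the first dose, and count it as treatment-emergent only if it exceeds the baseline grade.
- Add a shift table of baseline grade by worst post-dose grade.
- Apply the same post-dose window to every column, and state that the Week 0 pre-dose draw is never an on-treatment value. Non-fasting glucose keeps its screening baseline.
- State that the Week 16 pre-dose draw counts under placebo and is the baseline for the two crossover columns. SAP 2.7 would otherwise leave their baseline at Week 0.

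The cost is SAP wording and one additional table shell, using data already collected. Crude abnormality counts will be lower, but the display of all laboratory reports planned in SAP 6.2 still shows every abnormal value.
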